5.2.3.2 Methotrexate

For the RIC cohort (FluBu2)- The methotrexate dose will be 5 mg/m² IV on day+1,3,6,11, infused as per standard institutional guidelines. In cases where stem cell infusion (day 0) spans more than 1 day, the day +1 dose of methotrexate

should start 1 day after the end of the SC infusion.

For the Myeloablative cohort (FluBu4)- The methotrexate dose will be 15 mg/m² IV on day +1, and 10mg/m² on days +3,6, and 11. Methotrexate should be infused as per standard institutional guidelines. In cases where stem cell infusion (day 0) spans more than 1 day, the day +1 dose of methotrexate should start 1 day after the end of the stem cell (SC) infusion. Leucovorin rescue is allowed per standard practice guidelines if necessary, at the discretion of the transplant physician. The day 11 dose of MTX may be reduced 50% or omitted if deemed necessary based on the clinical situation, and at the discretion of the transplant physician. In cases where clinical toxicities, e.g. renal failure, pleural effusion, etc. would render completing at least 3 doses of methotrexate unsafe, substitution with mycophenolate mofetil (cellcept) 1000mg PO/IV BID or other agent such as sirolimus is allowed at the discretion of the treating physician. In instances where MTX is substituted by cellcept, it is recommended that the cellcept be discontinued around day +28 in the absence of GVHD.

5.2.4 Tacrolimus Taper:

- 5.2.4.1 Tacrolimus taper is NOT allowed during the vaccination period. Taper may commence 1 week after the last GVAX/Placebo vaccine, at the discretion of the transplant physician, with the goal to be off immune suppression by 6-9 months in the absence of GVHD.
- 5.2.4.2 **Tacrolimus taper for patients with progressive disease before completion of vaccinations**: Patients with evidence of progressive disease AND requiring additional therapy or taper of immune suppression will receive no further vaccinations. In these cases, the tacrolimus taper will be performed at the discretion of the treating physician.

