5.3 GVAX/Placebo Vaccination

Vaccination with GVAX or placebo vaccine will commence after hematologic recovery has occurred and the patient is between day +30 to day +60* post transplant. Vaccine administration can occur on an either inpatient or outpatient basis. At any time between day+30 to day +60*, the patient may undergo a bone marrow aspirate/biopsy and GVAX/placebo vaccination may commence provided the following criteria are satisfied:

* Day 60 or next business day, if day 60 occurs on a weekend or holiday

5.3.1 Criteria for starting GVAX/Placebo administration:

- No grade II-IV acute GVHD
- No systemic corticosteroid therapy*
- No uncontrolled acute infection
- No CTC grade ≥ 3 non-hematologic toxicity
- Absolute neutrophil count $\geq 500/\text{ul}$ off growth factor

- Platelet count ≥ 10 K/ul without transfusion.
- Absolute eosinophil count ≤ 5000/ul

Participants who do not meet the above criteria to start vaccination by day +60 will be considered "off treatment", and followed for survival.

5.3.2 **GVAX/Placebo Administration:**

- 5.3.2.1 Vaccinations will be administered weekly x 3 weeks, then q2weeks x 6 weeks for a total of 6 vaccines. The weekly scheduling of vaccination can be +/- 2 days for scheduling flexibility. A physician, PA, NP, RN, or research RN can administer the injections in either an outpatient or inpatient clinical setting. Injections will be administered according to standard nursing procedure in the patient's arms and thighs on a rotating basis. Injections must be performed without the prior application of EMLA or other topical or local anesthetics, as such compounds both could obscure local reactions to the vaccination and could cause reactions that might be interpreted as vaccine reactions. Approximately half of the vaccine dose should be administered subcutaneously, and remaining half the vaccine dose intradermally. It is suggested that about half of the vaccine be given first intradermally, and the rest subcutaneously by changing that angle of the needle.
- 5.3.2.2 Information regarding the number and location of the injections, the date of vaccination, route of administration, total volume of vaccine administered and vaccine site injection reactions will be collected for each vaccination and recorded in the patient medical record.

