5.3.3 Early discontinuation of GVAX/Placebo vaccination

- 5.3.3.1 Disease relapse or progression requiring taper or withdrawal of tacrolimus, or additional systemic therapy.
- 5.3.3.2 Acute GVHD or chronic GVHD requiring systemic steroid therapy.
- 5.3.3.3 CTC grade ≥ 4 non-hematologic toxicity possibly, probably or definitely related to vaccination.
- 5.3.3.4 Delay of vaccination over 14 days (see below)

^{*} Except for physiologic doses of steroids for adrenal insufficiency

- 5.3.4 **Delay of GVAX/Placebo vaccination**: If severe hematologic toxicity (defined as ANC <500/ul, platelet < 10K/ul, or absolute eosinophil count > 5000/ul), CTC grade ≥ 3 non-hematologic toxicity develops during the vaccination period, vaccination may be delayed up to 14 days until the event has improved by at least 1 CTC grade. If condition is not improved after 14 days in the opinion of the treating physician and/or study PI, or if the toxicity recurs upon reinitiation of vaccination, no further vaccination will be given. In an event where the toxicity is grade < 3, vaccination may also be delayed at the physician's discretion.
- 5.3.5 **Off Treatment Criteria with continued study visits**: Patients who receive at least 1 vaccination, but do not complete 6 vaccines for any reason other than disease relapse requiring additional therapy or hospice will be considered "off treatment". These patients will continue "on study" for study visits, tests/procedures, and assessment of toxicity and survival end points. It is preferred that study specific blood samples be drawn and bone marrow biopsies are performed according to the study calendar, but these may be foregone for clinical reasons or if the patient declines to have one performed.
- 5.3.6 **Off Treatment Criteria with survival follow-up only**: Patients meeting the following criteria will be considered "off treatment" and no further study visits, or study related testing will be performed. Survival information will be recorded.
 - 5.3.6.1 Patients who have disease relapse after starting vaccination and require additional therapy (chemotherapy or immune therapy) or hospice placement.

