12.0 STATISTICAL CONSIDERATIONS

12.1 Endpoints

12.1.1 **Primary Endpoint**: The primary endpoint of this study is progression-free survival (PFS) at 18 months post-randomization. Progression-free survival is defined as time from randomization to progression of disease or death whichever occurs first. Patients with relapse/progressive disease who re-enter remission after vaccination or upon withdrawal of immune suppression alone will not be considered as having disease progression. The primary analysis will be performed using the modified intention-to-treat (ITT) principle, i.e., all transplanted and eligible patients who receive at least one vaccination will be included in the analysis according to the treatment arm they are randomized to.

12.1.2 **Secondary Endpoints**

- 12.1.2.1 Safety and toxicity of vaccination, as measured by the development of:
 - Grade II-IV and III-IV acute GVHD
 - CTC grade \geq 3 non-hematologic toxicity, or

- Grade \geq 4 hematologic toxicity attributable to vaccination
- 12.1.2.2 Biologic responses to vaccination following allogeneic stem cell transplant, as assessed by laboratory and histologic analyses of blood before and after vaccination, and skin biopsy samples at vaccination sites (Section 8.0). Serum and circulating mononuclear cells will be frozen prior to beginning vaccination and at regular intervals thereafter. Bone marrow aspirates will also be cryopreserved, if sufficient material is available.

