12.5 Sample Size and Power Calculations

In our previous study¹⁰, the 2-year progression-free survival for 15 patients who received at least one vaccination was 46%. This estimate compared to 18% 2-year PFS from our contemporaneous control cohort that was most similar to those patients in the GVAX trial. Extrapolating this information, we hypothesize that the PFS will be increased by 75% at 18 months post randomization in Arm A (GVAX) compared to Arm B (placebo). A retrospective analysis of high risk AML/MDS patients who underwent myeloablative or RIC HSCT between 2004 and 2008 at DFCI shows that a small portion of patients are cured from the underlying disease after allogeneic HSCT and the distribution of PFS follows a two-component exponential cure rate model (Figure 1). Basing the fitted curve in Figure 1 as the null hypothesis, we hypothesize that the PFS will be increased by 75% from 26% to 46% by 18 months post HCT in Arm A. More specifically, the proposed alternative hypothesis is H_A: S_A > S_B,

where S_A and S_B denote the distributions of PFS in Arms A and B, as shown in (1) and (2), respectively

$$\begin{split} S_A &= 0.45 + 0.45 * exp(-t*(log(2)/2.5)) + 0.1*exp(-t*(log(2)/4.5)) \ (1) \\ S_B &= 0.24 + 0.76 * exp(-t*(log(2)/3.5)) \end{split} \tag{2}$$

This projection incorporates approximately 30-45 days of wait time from randomization to the start of GVAX/Placebo vaccination and additional ~40 days for the administration of a serial of 6 vaccinations. During this period, we expect little difference in PFS between two arms. Figure 4 depicts (1) and (2) graphically. With this design, 106 eligible patients with 69 events will be required to achieve approximately 80% power with one-sided significance level of 0.15. Since this is a direct but nondefinitive randomized comparison to a standard treatment control, we follow recommendations made by Rubinstein et al. ^{18, 19} and use a one-sided type I error rate of 0.15 with 80% power ¹⁸⁻²⁰. The power calculation is calculated using the R program, *Powlgrnk* (developed by [name] at DFCI), which computes power of the two-group log-rank test for arbitrary failure time distributions and has been used for non-proportional hazards alternative.²¹

[figure not shown]

Figure 4. Target PFS. Blue line represents the projected PFS distribution in Arm A (GVAX) and red line represents the projected PFS distribution in Arm B (Placebo). The solid black line is the Kaplan-Meier curve from the historical control

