12.8 Statistical Analysis Plan

The primary analysis will be the modified ITT analysis for the primary endpoint of PFS at 18 months after randomization. The primary analysis will be performed using the Kaplan-Meier estimates for PFS for each arm at 18 months along with 95% confidence intervals. Several secondary analyses of PFS will be conducted, depending on an assessment of the original assumption of non-proportional hazards assumed in the study design. First of all, graphical and analytical diagnostics will be used to assess the presence of non-proportional hazards between treatment arms. If there is no evidence of nonproportional hazards, a relative risk will be estimated from the Cox model both unadjusted and adjusted for other covariates. To assess the effect of GVAX, several approaches will be taken: 1) inclusion of the treatment arm as a fixed covariate in a model, 2) inclusion of the total number of GVAX vaccinations (0-6) as a fixed covariate in a model, 3) treating the number of GVAX/placebo vaccinations as a time dependent repeated measures and an interaction between the number of vaccinations and the treatment arm in a model, 4) exploring a joint model for survival and longitudinal data. 26 If there appears to be non-proportional hazards, several analyses will be conducted: 1) a comparison of PFS at 18 months post randomization will be conducted using the linear combination test proposed by Logan et al.^{24, 28.29} This method directly compares the PFS curves starting at 18 months, and accounts for patients enrolled early in the study having additional follow-up past 18 months. 2) a pseudo value regression approach³⁰, 3) PFS from the start of vaccination will be analyzed, 4) multivariable cure rate model will be performed as described in Ibrahim et al.²⁷

Secondary objectives include relapse and non-relapse mortality (NRM), acute and chronic GVHD, overall survival. For the comparison of GVHD, NRM and relapse, we will perform competing risks data analysis using Gray test and competing risks regression analysis.²⁵ All laboratory correlative studies will be analyzed using appropriate statistical methods. In particular, the effect of vaccination on infiltration of dendritic cells, macrophages, granulocytes, and lymphocytes as well as T cell reconstitution will be examined by comparing pre to post vaccination data and the GVAX to the

placebo arm.

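### The secondary Cox model on total GVAX doses uses a covariate that PFS events themselves cut short, which biases that model towards GVAX

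*Combined protocol and SAP*

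**What the plan says.** Section 12.8 makes the primary analysis the Kaplan-Meier estimates of PFS at 18 months by arm in the modified intention-to-treat set. Secondary analyses then depend on a check for non-proportional hazards between the arms: "If there is no evidence of nonproportional hazards, a relative risk will be estimated from the Cox model". For that case, four ways of measuring the GVAX effect are listed:

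1. treatment arm as a fixed covariate;
2. "inclusion of the total number of GVAX vaccinations (0-6) as a fixed covariate in a model";
3. the vaccination count as a time-dependent measure, with an arm interaction;
4. a joint survival and longitudinal model.

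The four are not ranked, and approach 2 carries no landmark or other safeguard.

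Three other rules bear on approach 2:

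- **Clock.** Section 12.1.1: "Progression-free survival is defined as time from randomization to progression of disease or death whichever occurs first". It does not count as progressed those patients "who re-enter remission after vaccination or upon withdrawal of immune suppression alone will not be considered as having disease progression".
- **Dosing span.** Section 1.1 puts the six doses on days 0, 7, 14, 28, 42 and 56 from the first. Section 12.5 allows "additional ~40 days for the administration of a serial of 6 vaccinations".
- **Stopping.** Section 5.3.3.1 ends vaccination for "Disease relapse or progression requiring taper or withdrawal of tacrolimus, or additional systemic therapy". Section 5.2.4.2 says that patients with progression "requiring additional therapy or taper of immune suppression will receive no further vaccinations".

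**The concern.** A fixed covariate in a Cox model is treated as known at time zero. The total dose count is not known then. A GVAX patient who dies, or who has a dosing-ending progression, between days 14 and 28 is fixed at 3 doses. Only a patient who escapes such an event until day 56 can score 6. High counts are in part a record of having stayed event-free, which is immortal-time bias.

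Placebo patients face the same stopping rules but all score 0. The distortion therefore enters only through the GVAX arm, where early events go with low counts, and it pulls the slope towards benefit. Adjustment for baseline covariates cannot correct a covariate that the outcome helps to set.

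At stake is a secondary result that shows a benefit and a dose-response for an inert vaccine, reported beside a null comparison by arm, with nothing in the plan to say which Cox model to believe.

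**Working it through.** **Design check.** Section 12.5 gives, with t in months, S_B(t) = 0.24 + 0.76·exp(−t·ln2/3.5) for placebo, and a three-component curve for GVAX. At 18 months these give 26.2% and 45.9%. A simulated log-rank test with 53 per arm, 3.8 years of accrual, 18 months of further follow-up and one-sided 0.15 gives 81.3% power and 69.2 expected events. The plan's 80% and 69 are reproduced.

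**How many events fall in the dosing window.** Take a patient who is event-free at 1.25 months, the middle of the 30–45 day wait in Section 12.5. Fifty-six days is 56/30.4375 = 1.84 months.

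- S_B(1.25) = 0.24 + 0.76·exp(−0.248) = 0.833
- S_B(3.09) = 0.24 + 0.76·exp(−0.612) = 0.652
- P(event in window) = 1 − 0.652/0.833 = 21.7%

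Starts at 0 and 2.5 months give 23% and 20%. In the pilot (Section 2.4.2), 3 of 15 vaccinated patients stopped for progressive leukemia (20%, exact 95% CI 4–48%). That is compatible, but too few to fix the share of PFS events that end dosing.

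**Null simulation.** Both arms follow S_B, with 53 per arm, all event-free at first dose, followed for 18–64 months, 4,000 trials per scenario (Monte Carlo SE at most 0.8 points). A stated share of PFS events in the window ends dosing. A further 13% stop for unrelated reasons (pilot: 2 of 15). The yardstick is the design's one-sided 15%; the plan assigns no level to approach 2.

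| Share of PFS events that end dosing | 56-day span: HR 6 vs 0; favours GVAX | 40-day span: HR 6 vs 0; favours GVAX | 56-day span at one-sided 2.5% |
|---|---|---|---|
| 100% | 0.78; 50% | 0.82; 40% | 16% |
| 60% | 0.86; 33% | 0.89; 28% | 8.5% |
| 30% | 0.93; 23% | 0.94; 21% | 5% |
| 0% | 1.0; 15% | – | – |

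Separately programmed repeats on the 56-day schedule gave 0.77–0.78 and 48–53% at share 100%, 0.85–0.86 and 32–35% at 60%, and 0.93 and 22–23% at 30%.

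**Comparators on the same data.** The arm model, a time-dependent count and an end-of-window landmark count gave HR about 1.0 and 14–15%. Approach 3 with its interaction term stayed at HR about 1.0, with 12–17% for it and the arm model together.

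**Sensitivity.**

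- Without unrelated stops, share 100% gives 0.77 and 53–55%.
- If 20–40% of dosing-ending progressions re-enter remission and so are not PFS events, share 100% gives 0.81–0.84 and 36–43%; share 60% gives 0.88–0.91 and 24–28%.
- If 10% of vaccinated patients had already progressed before dose 1 (an assumed figure), shares 100/60/30% give 0.82/0.89/0.94 and 41/28/21%. With 20%, they give 0.88/0.92/0.97 and 31/24/19%.
- Under the design's GVAX curve, approach 2 gives HR 0.42 at share 100%, against 0.55 at share 0 and 0.56 for arm. It would exaggerate a real effect too.

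**Does the proportional-hazards condition protect?** No. With an inert vaccine the hazards by arm are proportional, so the Cox branch is normally entered. In the simulation 95% of null trials pass a 5% scaled Schoenfeld residual test by arm (assumed; the plan names no test), and the rates among them are again 50, 33 and 23%.

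**The case against.** The strongest reply concerns weight, not mechanism.

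- **Hierarchy.** Section 12.8 names a primary analysis by randomized arm and calls the rest secondary, so the plan is not silent on what comes first. This stands. What is missing is a ranking among the four Cox approaches.
- **Consequence.** Approach 2 would be reported beside the arm model and a time-dependent count, and nothing in the documents ties a decision to it. This also stands, and it limits the severity.
- **The 50% figure is the extreme.** Progression that needs neither taper nor therapy does not stop dosing, and relapses that re-enter remission are not events. The start criteria in Section 5.3.1 set no disease-status condition, so some patients may progress before dose 1 and still receive every dose. Section 9.0 schedules marrow examinations at vaccine 1 and one month after the last vaccine, with none between, so progression seen only in marrow may be dated after dosing. All of this is fair and shrinks the bias. As a guide, with an SE of about 0.24 for the 6-versus-0 log hazard ratio, the bias is about 1.0, 0.6 and 0.3 SE at shares 100, 60 and 30%. None of it reverses the direction.
- **Approach 3 already covers dose.** It is listed in addition to approach 2, not in its place. Its presence shows that a sounder form of the question is available.
- **Deletion is more than needed.** Labelling the model exploratory would reduce misreading, but the estimate would still be biased, and it answers nothing that approach 3 does not answer better.

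**Conclusion.** Approach 2 is wrong as written. Its covariate is partly determined by the outcome, and the bias favours GVAX whenever some PFS events in the dosing window end dosing. On the 56-day schedule the apparent hazard ratio for 6 versus 0 doses under no effect runs from 1.0 (share 0) to 0.78 (share 100%). The chance of favouring GVAX at a nominal 15% runs from 15% to 50%. A 40-day span, the remission exemption or progression before dose 1 gives smaller figures in the same direction.

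The result rests on placebo curve (2) holding in both arms, on stops for other reasons being unrelated to PFS, and on a share that the documents do not supply, which is why the full range is given. The pilot shows that the link is real: 5 of 15 vaccinated patients did not complete, 3 of them for progressive leukemia. Nine of the 15 were alive in remission and 9 of the 10 completers were in remission, which leaves none of the 5 non-completers.

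The damage is confined to this one secondary model. The primary Kaplan-Meier comparison, approach 1 and the stated power are untouched. The change should be made, but the trial's main conclusion does not depend on it.

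**What to change.** Delete approach 2 from Section 12.8. State that the comparison by randomized arm carries the efficacy conclusion: the primary analysis, and approach 1 within the Cox models. Examine dose-response only through the time-dependent count in approach 3, or through a landmark at the end of the vaccination window among patients still event-free. Label both non-randomized and exploratory, since neither removes confounding by patient condition.

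One detail for the time-dependent count: let risk time start at the first dose. With time counted from randomization and an assumed wait of 2–4 months, the simulated single-covariate version drifted the other way (HR 1.07, 10% favouring GVAX), because patients in the simulated set cannot fail before dose 1 yet contribute zero-dose time. With a 1–1.5 month wait and time counted from first vaccination it was 0.99 and 15%.

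The cost is wording only. Section 5.3.2.2 already records "the date of vaccination, route of administration, total volume of vaccine administered" for each vaccination. The landmark version loses patients who fail before it, about 15–23% under curve (2) depending on span and start. Sample size, conduct and primary analysis do not change.

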1.1 Study Design

GVAX vaccines will be generated by adenoviral vector mediated GM-CSF gene transfer into myeloblasts harvested from study subjects prior to admission for hematopoietic stem cell transplant Patients with Myelodysplastic syndromes (MDS) with excess marrow blasts or Acute myeloid leukemia (AML) not in remission are eligible. Leukemia cells will be harvested for vaccination generation after enrollment. Patients will be randomized (1:1) to GVAX versus placebo arm prior to The assignment of treatment arm will be blinded to the patients, treating transplant admission. physicians, nurses, research staff, and data assessors. Between the leukemia cell harvest and admission for allogeneic HSCT, patients are allowed to receive additional therapy (e.g. HMA therapy, chemotherapy etc.) at the discretion of the treating physician. Between day+30 to +60* after HSCT, patients with adequate hematologic recovery and no GVHD requiring systemic therapy will receive GVAX or placebo vaccine (normal saline) injections weekly x 3 week, then starting on week 5, every 2 weeks for 6 weeks, to complete a set of six total vaccinations. Patients will remain on tacrolimus for GVHD prevention during the vaccination period. Tacrolimus taper may commence after completion of vaccination, at the discretion of the treating physician, with the goal to be off immune suppression by 6-9 months post transplant in the absence of GVHD.

* Day 60 or next business day, if day 60 occurs on a weekend or holiday

1.2 **Primary Objective:**

Progression-free survival (PFS) at 18 months after randomization

1.3 Secondary Objectives:

- a) To assess the safety of vaccination following allogeneic (ablative or reduced intensity) stem cell transplantation
- b) To assess incidence of grade 2-4 and grade 3-4 acute GVHD, and chronic GVHD after vaccination following allogeneic stem cell transplantation.
- c) To assess PFS after start of vaccination
- d) To assess relapse and non-relapse mortality after vaccination
- e) To assess overall survival after vaccination
- f) To assess biologic activity of GVAX as compared to placebo vaccination after HSCT (see Section 8.0)

CONFIDENTIAL

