2.2 Study Disease: Allogeneic SCT for Advanced MDS/AML

Although allogeneic hematopoietic stem cell transplantation is a potential curative therapy for patients with advanced hematologic cancers, disease relapse remains the single most frequent cause of treatment failure. Success of allogeneic HSCT relies heavily on the development of anti-tumor activity generated by the new donor derived immune system post transplant, also known as the graft-versus-tumor effect (GVT). Attempts to enhance GVT by early withdrawal of immune suppression or administration of donor lymphocyte infusions (DLI) have been hampered by increased rates of graft-versus-host disease (GVHD). Strategies to safely inducing GVT without promoting GVHD are needed.

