- 6.1.1.7 **Acute and chronic GVHD**. While we hypothesize that this vaccine may elicit a leukemia specific response by the donor immune system, the possibility that it may elicit or aggravate GVHD also exists. In our previous trial using this GVAX platform after RIC SCT (04-023), we did not observe any increase in acute or chronic GVHD in excess of what is expected at baseline. Differences in grade 3-4 acute GVHD between the vaccine and no vaccine arms will be assessed in planned interim analyses, see section 13.7.
- 6.1.1.8 **Unexpected vaccine related toxicity**: Any severe adverse event (CTC grade ≥ 3) that is not readily explained as a transplant or disease associated complication will be assessed as a possible vaccine related toxicity.

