12.2 Study Design and Objectives

This is a randomized placebo controlled Phase II study of GVAX versus placebo vaccination given early after allogeneic HSCT in high risk AML/MDS patients. The premise is that GVAX vaccination early after HSCT will increase progression-free survival (PFS) in this patient population. The target accrual goal is 106 eligible patients for vaccination, 53 per each arm, over a 3.8 year period and followed for an additional 18 months. This design will give approximately 80% power to detect a 75% increase in 18 month PFS in the GVAX arm (Arm A) compared to the placebo arm (Arm B) as graphically illustrated in Figure 1.

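### Section 12.8 compares chronic GVHD on cumulative incidence, which fits the incidence objective but cannot by itself show whether GVAX elicits GVHD; a cause-specific comparison should be named alongside it

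*Combined protocol and SAP*

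**What the plan says.** - **Analysis (section 12.8).** "For the comparison of GVHD, NRM and relapse, we will perform competing risks data analysis using Gray test and competing risks regression analysis". The section does not say which events compete with GVHD, whether the regression models the subdistribution or the cause-specific hazard, or what significance level applies to chronic GVHD. No cause-specific comparison is named.
- **Objective (section 1.3(b)).** "To assess incidence of grade 2-4 and grade 3-4 acute GVHD, and chronic GVHD after vaccination following allogeneic stem cell transplantation".
- **Safety question (section 6.1.1.7).** The vaccine is meant to raise a leukemia-specific response, but "the possibility that it may elicit or aggravate GVHD also exists". Section 2.2 gives the aim behind it: "Strategies to safely inducing GVT without promoting GVHD are needed".
- **Design hypothesis (section 12.5).** "we hypothesize that the PFS will be increased by 75% from 26% to 46% by 18 months post HCT in Arm A", with explicit PFS curves for both arms.
- **Follow-up after relapse (section 5.3.6).** A patient who relapses after starting vaccination and needs further therapy or hospice has no more study visits or testing; only survival is recorded. Section 11.1.2 has transplant data collected in the BMT repository for everyone enrolled.
- **Level (section 12.7).** A two-sided 0.05 is given, but only for interim comparisons of grade III-IV acute GVHD and treatment-related toxicity.

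**The concern.** Asking whether GVAX elicits GVHD is asking whether patients still alive and relapse-free develop new GVHD at a higher rate on GVAX. Gray's test has a different null, equal cumulative incidence. Under it, a patient who relapses or dies first counts as never developing GVHD.

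The design assumes that the arms differ in exactly that respect. If GVAX prevents relapse, more GVAX patients remain at risk during the months when chronic GVHD could appear. Their cumulative incidence is then higher even if the vaccine does nothing to GVHD. The difference in incidence is real, but reading it as vaccine-induced GVHD would be wrong. The risk of that misreading is greatest when the vaccine works. The reverse can also happen: a true change in the GVHD hazard can be offset by the change in time at risk.

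**Working it through.** **Inputs from the documents**
- 53 patients per arm (section 12.2).
- PFS curves (section 12.5), t in months, written in powers of 2: S_A(t) = 0.45 + 0.45·2^(−t/2.5) + 0.10·2^(−t/4.5) and S_B(t) = 0.24 + 0.76·2^(−t/3.5).
- Chronic GVHD cumulative incidence of 47% in vaccinated pilot patients, 7 of 15 (section 2.4.2).

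**Assumptions, not in the documents**
- Relapse and death both compete with GVHD.
- GVHD timing is independent of relapse.
- The chronic GVHD hazard λ is constant within an onset window, zero outside it, and the same in both arms. The windows are varied.
- The level is two-sided 0.05, borrowed from section 12.7.
- Follow-up is complete to 18 months.

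**Step 1: reproduce the plan's figures.**
- S_A(18) = 0.45 + 0.0031 + 0.0063 = 0.459.
- S_B(18) = 0.24 + 0.0215 = 0.262.
- Simulating the log-rank test with 3.8 years of accrual plus 18 months gives 69.2 expected events and power 0.81 at one-sided 0.15. The plan states 69 events and about 80%.
- 106/0.70 = 151.4, so 152 enrolled, as in section 12.3.

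**Step 2: who remains at risk.**

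| Month | S_A | S_B | S_B/S_A |
|---|---|---|---|
| 3 | 70.9% | 66.0% | 0.93 |
| 6 | 57.5% | 47.2% | 0.82 |
| 12 | 48.2% | 31.1% | 0.64 |
| 18 | 45.9% | 26.2% | 0.57 |

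**Step 3: cumulative incidence under an identical hazard.** For onset window a to b, CIF = ∫ λ·exp(−λ(t−a))·S(t) dt from a to b. λ is chosen so that the GVAX arm reaches 47%, and the same λ is then used with S_B. For months 6-12, λ = 0.356 per month gives 47.0% v 35.5%. As a check, 35.5/47.0 = 0.76, which lies between the month-6 and month-12 ratios in step 2. For months 3-6, 41.8/47.0 = 0.89, because the arms have barely separated by then.

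**Step 4: how often each test rejects.** With no censoring before month 18, Gray's test is a log-rank test that keeps competing-event patients in the risk set. The cause-specific log-rank test censors them at relapse or death. Each row rests on 3,000 to 20,000 simulated trials.

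| Assumed onset (months from randomization) | Placebo CIF when GVAX is 47% | Gray rejects, 47% | Gray rejects, 30% |
|---|---|---|---|
| 3-6 | 42% | 8.4% | 6.6% |
| 3-12 | 39% | 12.5% | 9.6% |
| 4-12 | 38% | 15.1% | 11.7% |
| 3-18 | 37% | 17.3% | 13.8% |
| 6-12 | 36% | 20.9% | 14.8% |
| 6-14 | 35% | 22.5% | 17.0% |

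Nearly all rejections point to excess GVHD on GVAX, less uniformly so for early onset at low incidence. The cause-specific test rejects in about 4.5-6% throughout. With equal PFS in both arms, Gray's test rejects in 4.7-5.2%, so the PFS difference is what drives the excess.

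**Step 5: where the excess shrinks.**
- About half the PFS effect: roughly 6-10% at 47% incidence and 5-9% at 30%.
- Only death competes and GVHD is still assessed after relapse (assuming 80% of PFS events are relapses and a post-relapse median survival of 3-12 months): 5-11%.
- Relapse treated as censoring: about 5%.
- Acute GVHD with onset in months 2-5: 4.4-5.8%. NRM: 4.5-5.9%.

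**Step 6: the reverse case.** If GVAX lowered the chronic GVHD hazard by 30%, with onset in months 4-12, the formula in step 3 gives about 31% on GVAX v 30% on placebo. The reduction would not show on cumulative incidence.

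**The case against.** **The test fits the stated objective.** Section 1.3(b) asks for incidence, and the pilot benchmark is a cumulative incidence. In the scenarios above the incidences truly differ, so a rejection is a correct detection. A reader might infer that Gray's test is invalid here, or that it raises false alarms at two to four times its nominal rate. The documents do not support either. Section 12.8 never says that a Gray p-value will be read as the vaccine eliciting GVHD. The two-to-four-times figure also needs the full PFS effect, incidence near 47%, onset spread beyond months 3-6, relapse as a competing event, and a level the plan does not set for chronic GVHD. This objection stands. What remains is that the section 6.1.1.7 question has no named analysis.

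**A regression is also planned.** If it is cause-specific, most of the gap closes. Its type is not stated, so this needs one clarifying phrase.

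**Relapse as a competing event is inferred.** Section 5.3.6 ends visits only for relapse that needs therapy or hospice, and repository data continue for all. GVHD may therefore be known after relapse. This stands as a limit on the size. It is also a reason to name the competing events, because the rejection rate runs from about 5% to 23% depending partly on that choice. Section 5.2.4.2 leaves the tacrolimus taper to the physician's discretion after progression, so GVHD after relapse would not cleanly reflect the vaccine in any case.

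**The cause-specific result is not a clean arbiter.** A reader might want it to settle the causal question alone. It conditions on staying alive and relapse-free, which treatment is hypothesised to change, and section 2.2 links a stronger graft-versus-tumor effect to more GVHD. With an assumed correlation of −0.3 to −0.5 between GVHD and relapse times, and no vaccine effect on GVHD, its protective tail is 3.2-6.6% against 2.5%. The shift is modest, but it means both results must be read together.

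**Consequence is limited.** Chronic GVHD is one of several secondary outcomes in a phase II trial that section 12.5 itself calls nondefinitive, and no stopping rule depends on it.

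**Conclusion.** The point holds as a gap in interpretation; the planned test is not in error. Gray's test serves section 1.3(b), but on its own it cannot tell a vaccine effect on GVHD from an effect on relapse.

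Under the plan's own PFS curves and an identical chronic GVHD hazard, it rejects in about 8-23% of trials at 47% incidence and about 6-17% at 30%. That compares with about 5-6% for the cause-specific test. Even at the upper end, most trials would show no significant difference.

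The range rests on relapse and death competing, the full hypothesised PFS effect, assumed onset windows, independence of GVHD and relapse times, and an assumed two-sided 0.05. It falls towards 5% if onset is early, the PFS effect is about halved, or only death competes. Early acute GVHD and NRM are little affected. This is a cheap improvement.

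**What to change.** In section 12.8:
1. Name relapse and death as the competing events for GVHD, and state the type of the competing risks regression.
2. Keep the cumulative incidence curves and Gray's test as the measure of patient burden.
3. Add, for chronic GVHD, a cause-specific log-rank test and a cause-specific Cox hazard ratio with 95% CI. Report cause-specific hazard ratios for relapse and NRM beside it.
4. State that a difference in cumulative incidence alone will not be read as GVAX eliciting GVHD. The cause-specific result will be read with it, noting that it conditions on patients remaining alive and relapse-free.

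The cost is a few sentences and a few extra model runs on data already planned; no new patients or procedures are needed. The downside is two GVHD summaries to report and explain.
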